11.0 Data Review

11.1 Data Handling and Transfer

Please see the Data Management Plan.

11.2 Data Screening

Beyond the data screening built into the PPD Data Management Plan, the PPD programming of analysis datasets and TFLs provides additional data screening. Presumed data issues will be output into SAS logs identified by the word "Problem" and extracted from the logs by a SAS macro and sent to Data Management.

Review of dry run TFL allow for further data screening prior to lock. The **PPD** statistician and the sponsor must approve database lock.

12.0 Statistical Methods

All analyses will use SAS[®] version 9.4 or higher.

Subject data listings will be ordered by randomized or actual treatment ('Not randomized' / 'Not treated', 'BT524', 'FFP', 'Cryoprecipitate'), subject number (numerically, ascending) and visit of assessment respectively where applicable. All tables will be presented by treatment arm ('BT524', 'FFP/Cryoprecipitate') and overall. Where applicable tables will also be presented by treatment ('BT524', 'FFP', 'Cryoprecipitate') or by surgery (spinal, abdominal).

Unless otherwise noted, categorical variables will be summarized using number of observations (n), counts and percentages within category. Percentages will be rounded to one decimal place; except 100% will be displayed without any decimal places and percentages will not be displayed for zero counts.

Unless otherwise noted, continuous variables will be summarized using the number of observations (n), arithmetic mean, SD, minimum, Q1, median, Q3 and maximum. The minimum and maximum values will be displayed to the same level of precision as the raw data, the mean, median, Q1 and Q3 to a further decimal place and the SD to two additional decimal places. Unless stated otherwise the calculation of percentages will be based on the total number of subjects in the population of interest. Thus counts of missing observations will be included in the denominator and presented as a separate category.

The significance level will be 2.5% (one-sided), confidence intervals will be 95% (two-sided). All statistical tests (p-values) will be two-sided, unless otherwise stated.

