7.2.3 Safety

Safety and tolerability in this clinical study will be addressed by the following safety parameters:

- Frequency, severity, seriousness and causality of AEs.
- Changes in vital signs (including pulse [heart rate], blood pressure, respiratory rate, body temperature).
- Change in clinical laboratory assessments of hematology, clinical chemistry and urinalysis.
- Change in clinical laboratory assessments of markers of coagulation:

Prothrombin time (PT)/International Normalized Ratio (INR), activated partial thromboplastin time (aPTT), thrombin-antithrombin III complex (TAT), prothrombin fragments 1+2 (F1+2), D-dimer, protein S (PS), protein C (PC), antithrombin III (AT III), thrombin time (TT) and Endogenous Thrombin Potential (ETP) measured by Thrombin Generation Test (TGT) (TGT only for subjects undergoing cytoreductive PMP surgery).

• Change in clinical laboratory assessments of coagulation factors:

Factor II (FII), factor V (FV), factor VII (FVII), factor VIII (FVIII), factor IX (FIX), factor X (FX), factor XI (FXI), factor XIII (FXIII) and von Willebrand factor (vWF) (vWF only for subjects undergoing cytoreductive PMP surgery).

- Frequency, severity, seriousness and causality of thromboses and TEEs, of relevant bleeding complications, of Hypersensitivity/ anaphylactic reactions, and of bleeding related ischaemic events.
- Change in viral status.

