12.6.3 Laboratory Data

The following clinical laboratory variables will be summarized for the overall population, and separately by type of surgery (spinal and abdominal surgery):

Hematology	Red blood cells (RBC), white blood cells (WBC), platelet count, hemoglobin, hematocrit, neutrophils (absolute and %), lymphocytes (absolute and %), eosinophils (absolute and %) and basophils (absolute and %)
Biochemistry	Aspartate aminotransferase, alanine aminotransferase, creatinine, creatinine clearance (Cockcroft and Gault), blood urea nitrogen (BUN), urea, gamma-glutamyltransferase (γ -GT), alkaline phosphatase (AP), total bilirubin, direct bilirubin, indirect bilirubin, potassium, sodium, calcium and chloride
Urinalysis	pH, blood, WBC, protein, glucose, ketone bodies, nitrite, bilirubin and urobilinogen
Markers of Coagulation	PT, INR, aPTT, TAT, F1+2, D-dimer, PS, PC, AT III, TT and ETP(TGT)
Coagulation factors	FII, FV, FVII, FVIII, FIX, FX, FXI, FXIII and vWF

Note: Protein C (PC) is also referred to as Factor XIV. Direct bilirubin and indirect bilirubin are only assessed in case of an elevated bilirubin value and are thus not generally included in statistical summaries.

Quantitative laboratory parameters reported as "< x" or "y" > will be imputed with x/2 and y, respectively, for inclusion in summary statistics. The reported value will be presented in listings.

Descriptive statistics for clinical laboratory values (in SI units) and changes from baseline at each scheduled assessment visit (as stated in Flowchart of study) with the exception of urinalysis parameters and direct/indirect bilirubin will be presented by treatment and treatment arm.

Laboratory results of all hematology, biochemistry, urinalysis parameters and PT/INR, aPTT will be categorized with respect to the laboratory specific reference ranges as normal/abnormal (i.e., high [H], low [L], where applicable). Abnormal values will be further classified with respect to clinical relevance by the investigator. The results and percentages will be summarized by visit and overall for each treatment and treatment arm.

Shifts from baseline to each post-baseline visit for all laboratory variables (except direct and indirect bilirubin) will be summarized by treatment and treatment arm using number and percentage of subjects.

In addition, a shift summary of hematology for number of subjects with change from normal or not clinical significant to clinical significant will be presented.

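### In the overall-population shift table by treatment, vWF and ETP (TGT) percentages for BT524 are diluted by untested spine subjects, while those for cryoprecipitate are not

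*SAP*

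**What the plan says.** The default denominator is in SAP 12.0: "Unless stated otherwise the calculation of percentages will be based on the total number of subjects in the population of interest". The next sentence adds: "Thus counts of missing observations will be included in the denominator and presented as a separate category". Protocol 10.3 has the same rule. SAP 12.6 bases all safety analyses on the SAF, which holds every treated subject from both surgery types.

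SAP 12.6.3 opens its list of laboratory variables with "The following clinical laboratory variables will be summarized for the overall population, and separately by type of surgery (spinal and abdominal surgery". The list names vWF among the coagulation factors and ETP (TGT) among the markers of coagulation. For shifts it says "Shifts from baseline to each post-baseline visit for all laboratory variables (except direct and indirect bilirubin) will be summarized by treatment and treatment arm", as number and percentage of subjects. Protocol 10.7 asks for shift tables by arm only; the by-treatment columns come in with the SAP.

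SAP 7.2.3 restricts both tests: "TGT only for subjects undergoing cytoreductive PMP surgery" and "vWF only for subjects undergoing cytoreductive PMP surgery". SAP 12.6.3 leaves direct and indirect bilirubin out of the summaries because they are measured only in selected subjects. It makes no similar exception for the two PMP-only tests.

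**The concern.** In the overall-population table the three treatment columns are built from different surgery types. BT524 contains spine and PMP subjects, FFP spine only, and cryoprecipitate PMP only. For a test done only in PMP subjects, the default rule puts untested spine subjects in the BT524 denominator and none in the cryoprecipitate denominator. The two percentages then stand side by side on different bases, and the lower one belongs to BT524 even if the products behave alike.

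This matters because changes in coagulation markers and factors are named secondary safety endpoints. The protocol links raised vWF and thrombin generation to thrombosis risk (9.2.1.4) and names thrombosis as a risk of fibrinogen treatment (6.11). Cryoprecipitate itself contains vWF, so a reader is likely to look at BT524 against cryoprecipitate for these tests.

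**Working it through.** **The plan's own figure.** The documents give no shift percentages, so the only stated figure to reproduce is the arm size. With margin 150 mL, SD 375 mL, one-sided alpha 2.5% and 80% power, n = 2 × (1.960 + 0.842)² × 375² / 150² = 98.1, which rounds up to 99 per arm. The noncentral t distribution gives 80.4% power at 100 per arm. The stated 100 per arm reproduces. For 10% not in the PPS, 200 / 0.9 = 222.2, so 223, against the stated figure of about 220.

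**Inputs.**
- Total subjects N: 200 (evaluable) or 220 (randomised), from SAP 6.2, used as stand-ins for the SAF size.
- Allocation: 1:1 within spine and 1:1 within PMP (SAP 6.4). BT524 therefore has N/2 subjects, of whom P/2 are PMP, where P is the PMP total; cryoprecipitate has P/2.
- P: the documents give only at least 40 at the second interim analysis (SAP 10.0), with no final number or cap. Values from 40 to 120 are assumptions.
- r: the true shift rate among tested subjects, taken as equal under both products. The value 30% is an assumption for display.
- Complete testing of PMP subjects is assumed.

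**Formulas for the overall-population table.**
- BT524 column: r × (P/2) / (N/2) = r × P/N.
- Cryoprecipitate column: r × (P/2) / (P/2) = r.
- Factor, cryoprecipitate over BT524: N/P, which is total BT524 / PMP BT524. The rate r cancels; at 40 PMP of 200 the factor is 5.0 for r of 10%, 30% or 50%.
- Pooled FFP/cryoprecipitate arm: r × (P/2) / (N/2), the same as BT524.

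**Results at r = 30%.**

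| N | PMP total | BT524 tested / all | BT524 printed | Cryoprecipitate printed | Factor | BT524 not tested | Pooled FFP/cryoprecipitate arm |
|---|---|---|---|---|---|---|---|
| 200 | 40 | 20/100 | 6.0% | 30.0% | 5.0 | 80% | 6.0% |
| 200 | 60 | 30/100 | 9.0% | 30.0% | 3.3 | 70% | 9.0% |
| 200 | 80 | 40/100 | 12.0% | 30.0% | 2.5 | 60% | 12.0% |
| 200 | 100 | 50/100 | 15.0% | 30.0% | 2.0 | 50% | 15.0% |
| 200 | 120 | 60/100 | 18.0% | 30.0% | 1.7 | 40% | 18.0% |
| 220 | 40 | 20/110 | 5.5% | 30.0% | 5.5 | 82% | 5.5% |
| 220 | 100 | 50/110 | 13.6% | 30.0% | 2.2 | 55% | 13.6% |

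The factor reaches 3 only if PMP subjects number at most about 66 of 200 (200/3 = 66.7) or 73 of 220 (220/3 = 73.3).

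**The same data in the abdominal-surgery table.** Both columns have denominator P/2, so the result is 30% against 30%, a ratio of 1.0.

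**The case against.** Much of the case on the other side stands.

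- **The dilution would be visible.** The rule that causes it also requires missing observations to be shown as their own category. At 40 PMP of 200, the BT524 column would carry 80% missing and the FFP column 100%. This warns the reader but does not correct the printed percentages.
- **The right table is already required.** SAP 12.6.3 asks for the same summaries by surgery type, and the abdominal table compares PMP subjects with PMP subjects.
- **The planned contrast is not biased.** Protocol 10.3 treats FFP and cryoprecipitate as one group, and both pooled arms are diluted equally. All BT524 against cryoprecipitate in the overall table is not a randomised comparison in any case.
- **The wording leaves room.** The default applies unless stated otherwise, and for a PMP-only test the population of interest could be read as PMP subjects. The TFL specifications are separate documents, not available here, and may set another denominator. Against this, SAP 12.6 (SAF) and 12.6.3 (overall population) point to the wider denominator, and the SAP itself writes no exception.
- **The shift categories are unclear.** The classification sentence in 12.6.3, "Laboratory results of all hematology, biochemistry, urinalysis parameters and PT/INR, aPTT will be categorized with respect to the laboratory specific reference ranges", does not name vWF or ETP (TGT), so the exact layout of their shift tables cannot be predicted.

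Two stronger readings are tempting. A reader might infer that the SAP builds in a false safety advantage of BT524 over standard treatment. The documents do not support this: the artefact sits only in the by-treatment columns of one descriptive table, continuous vWF and ETP summaries rest on observed values, and thrombosis is assessed directly as an adverse event of special interest. A reader might also infer that the denominator should change for all laboratory and serology tables, because coagulation samples may be skipped when the 90-minute and end-of-surgery draws are under 30 minutes apart. Counting missing values as a displayed category is a recognised convention. No imbalance between arms is shown, the documents give no frequency of skipped samples, and the allowance does not cover serology.

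**Conclusion.** The point holds in a narrow form. Read literally, SAP 12.0 with 12.6.3 and 7.2.3 yields an overall-population shift table in which the BT524 percentages for vWF and ETP (TGT) are too low, relative to cryoprecipitate, by the factor total BT524 / PMP BT524. The existence of the artefact follows from the text. Its size rests on an assumed PMP share, on 1:1 allocation being achieved within each surgery type, and on complete testing of PMP subjects: about 5-fold at 40 PMP of 200, 2.5-fold at 80 and 2-fold at 100. The percentages in both pooled arms are also too low, by the same factor, so that comparison shows no false difference. No test, decision rule or primary conclusion depends on these tables. Severity is low.

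**What to change.** Add one sentence to SAP 12.6.3, in either form:

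- present vWF and ETP (TGT) shifts only in the abdominal-surgery tables; or
- base their percentages on PMP subjects in the SAF who have both a baseline and a post-baseline result, and show the number without a result as a count.

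The first is simpler, because those tables are already planned. The general denominator rule can stay as it is for all other laboratory and serology tables. The cost is the sentence and the matching table shells; no new data are needed. Because the default in both documents gives way to an explicit statement, the SAP can make this exception without conflicting with Protocol 10.3.

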12.1 Subject Disposition

The number of subjects screened and, the number and percentage who failed screening prior to surgery or during surgery, together with the main reasons, will be summarized for the All Subjects Enrolled Set. The number of subjects randomized, number and percentage of subjects treated with IMP, number and

percentage of subjects whose treatment was unblinded during the surgery will be summarized by treatment, treatment arm and overall for the All Subjects Enrolled Set. The subject disposition summary will be repeated for spinal and abdominal surgery.

The number of subjects included in each subject analysis set will be summarized by treatment arm and overall for the SAF. The number and percentage of subjects who completed the study or prematurely withdrew/discontinued from the study with the reason for withdrawal/discontinuation will be summarized by treatment, treatment arm and overall for the SAF.

The number and percentage of subjects treated at each country and center will be summarized by treatment, treatment arm and overall for the SAF.

A listing of details of whether the patients completed or discontinued study prematurely will be presented for the SAF. The informed consent and eligibility will be listed for the All Subjects Enrolled Set. The randomization data will be listed for the All Subjects Enrolled Set. A listing of analysis set allocation will also be created for the All Subjects Enrolled Set.

12.2 Protocol Deviations

Deviations from the CSP will be documented on an on-going basis during conduct of the clinical study based on monitoring reports (e.g., failure of eligibility criteria), data management checks and statistical programming (e.g., prohibited medications based on drug codes). Protocol deviations will be discussed and agreed in the BDRM to find PDs with major impact on subject safety or the validity of the study data. Subjects with major PDs will be excluded from the PPS under the assumption that the deviation may have an impact on the efficacy analysis.

In general, PDs will be considered according to the following general categories:

- Inclusion criteria
- Exclusion criteria
- Study drug
- Assessment safety
- Laboratory/ endpoint data
- Visit window
- Prohibited concomitant medications
- Overdose/ misuse
- Informed consent
- Other

Protocol deviations will be summarized by treatment arm and overall and listed for the FAS. The protocol deviation summary will be repeated for spinal and abdominal surgery.

12.3 Treatments

12.3.1 Extent of Study Drug Exposure

After a bleeding (risk) assessment only subjects requiring hemostatic treatment (high risk for the need of fibrinogen supplementation with BT524 or FFP/cryoprecipitate) during surgery, will be randomized and treated with BT524 or FFP/cryoprecipitate. If the bleeding remained unchanged and an ongoing relevant blood loss will be confirmed or the hemostatic control is not considered sufficient and requires further intervention or a new major blood loss occurred in the course of the surgery, subjects can be treated with repeated IMP administration according to their randomized treatment group.

As the IMP (BT524 or FFP/cryoprecipitate) will be administered intravenous (IV) to each subject under the supervision of the unblinded anesthesiologist, the compliance is expected to be 100%. In addition, the assessment of plasma fibrinogen concentrations may also serve as an adherence measure.

Exposure of IMP will be summarized by treatment separately for the SAF and repeated by surgery type (spinal or abdominal).

Descriptive statistics will be provided by treatment for the

- number and frequency of IMP administration(s) during surgery
- planned volume of IMP for each (1st, 2nd, ...) infusion
- actual volume of IMP administered for each (1st, 2nd, ...) infusion
- total planned volume of IMP administered during surgery
- total actual volume of IMP administered during surgery
- time to start of first IMP infusion
- duration of each (1st, 2nd, ...) IMP infusion
- number of interruption(s) during surgery for those subjects whose treatment administration was interrupted for the SAF
- actual gram of IMP (BT524) received by type of surgery and total

A listing will be created by subject number for infusion administration of IMP for the SAF.

12.3.2 Prior and Concomitant Medications or Treatment

The most updated version of the World Health Organization drug dictionary will be used to classify prior and concomitant medications by preferred term. Medications will also be coded with the lowest available Anatomical Therapeutic Chemical (ATC) classification system (level 4 to level 2).

Prior medication is defined as any medication with start date prior to IMP start date, irrespective of the stop date. Prior medications will be summarized by ATC classification and preferred term in treatment arms and overall for the SAF. The number and percentage of subjects using each medication will be displayed together with the number and percentage of subjects using at least one prior medication within each medication group and subgroup. This will be repeated by surgery type.

Concomitant medication is defined as any medication taken on or after the start date of IMP, irrespective of start date. Any concomitant treatment (surgeries or procedures) will be coded as "All Other Therapeutic". Concomitant medications/treatment categorized by ATC classification and preferred term will be summarized by treatment arm and overall for the SAF. The number and percentage of subjects using each medication will be displayed together with the number and percentage of subjects using at least one medication within each medication group and subgroup. This will be repeated by surgery type.

A medication can be both prior and concomitant if it was taken both prior and on or after the date of IMP.

In addition, prohibited medications will be tabulated.

All prior and concomitant medications will be listed separately for the SAF.

12.3.3 Medical and Surgical History, and Concomitant Disease

Medical and surgical history, and concomitant disease will be coded using the most updated version of the MedDRA® dictionary. Medical and surgical history until signature of informed consent, and concomitant disease will be summarized separately by MedDRA system organ class and preferred term in treatment arms and overall for the SAF. These will also be repeated by surgery type.

A listing of medical and surgical history, and concomitant disease will be created for the SAF.

12.3.4 Transfusion Products

The type of transfusion products includes autologous blood transfusion/cell salvage, allogenic platelet concentrates, allogeneic RBCs, allogeneic FFP, cryoprecipitate and other.

The number and percentage of subjects, using any transfusion products will be summarized by treatment and treatment arm for the SAF. This will be repeated by surgery type. The number and percentage of subjects will also be presented for each type of transfusion product. The volume (mL) of administration for each type of transfusion product will be summarized as well. This will also be repeated by surgery type. These summaries will also be performed separately for RBCs taken before start of first IMP (SAF) and for each type of transfusion product after start of first IMP (SAF). Transfusion products will be listed for the All Subjects Enrolled Set.

12.4 Demographic and Baseline Characteristics

Descriptive summaries of demographic and baseline characteristics will be presented by treatment, treatment group and overall, for FAS, mFAS, SAF and PPS. The following demographic characteristics will be summarized in the following order in the tables: sex, race, ethnicity, age, weight, height, body mass index, childbearing potential, and predictive blood loss. The summary will also be repeated for surgery type.

A listing will be created to show all the demographic and baseline characteristics for the All Subjects Enrolled Set.

A listing will be created to show results for pregnancy test of female subjects with childbearing potential for the SAF.

12.4.1 Surgery

The detailed information of surgery, including e.g., type of surgery (categorized by spinal and abdominal), predictive blood loss, duration of surgery, time until decision to treat subject, time to end of surgery after decision to treat, and overall vital signs monitoring during surgery will be listed for the All Subjects Enrolled Set. Number and percentage of subjects for each type of surgery, descriptive statistics for duration of surgery, time until decision to treat (relative to start of surgery), time to end of surgery (relative to time of decision to treat) and time of IMP exposure during surgery will be presented by treatment group and overall for FAS. The surgery summary, without type of surgery will be repeated for spinal and abdominal surgery.

12.5 Efficacy Analyses

12.5.1 Primary Efficacy Parameter

The primary efficacy parameter is the intra-operative blood loss after decision to treat the subject with IMP until the end of surgery as measured and calculated by amount of blood from the blood suction unit and amount of blood from swabs, surgical cloths and compresses.

The primary objective of this study is to demonstrate that BT524 is non-inferior that means not worse than FFP/cryoprecipitate with a non-inferiority margin of 150 mL in reducing intra-operative blood loss by intravenous (IV) administration in subjects with acquired hypofibrinogenemia undergoing elective major spinal or abdominal surgery. The primary analysis of this endpoint is a non-inferiority test in the PPS. The null hypothesis for the primary analysis is that the degree of inferiority of BT524 compared to standard treatment (FFP/cryoprecipitate) is greater than or equal to the non-inferiority margin. The alternative hypothesis is that the degree of inferiority of BT524 compared to standard treatment.

where

- μ 1 = mean intra-operative blood loss after the decision to treat the subject with IMP in the BT524 treatment arm
- μ2 = mean intra-operative blood loss after the decision to treat the subject with IMP in the FFP/cryoprecipitate treatment arm
- δ = non-inferiority margin = 150 mL

The final analysis will be performed using a two-way analysis of variance (ANOVA) with the intra-operative blood loss after the decision to treat the subject with IMP until the end of surgery as the dependent variable

and the predictive blood loss (> 1,000 mL to \leq 2,000 mL and > 2,000 mL) as a covariate. The least square means and treatment difference (BT524 versus FFP/cryoprecipitate) will be presented with the corresponding 2-sided 95% confidence intervals and p-value. Non-inferiority will be demonstrated if the upper confidence limit of the 95% confidence interval for the difference in the least square means is less than the non-inferiority margin (150 mL). Assumptions for the ANOVA model will be evaluated by diagnostic (e.g., Shapiro-Wilk test for normality) and graphical methods such as residual plots, including distribution of residuals, and Q-Q plots of residuals. The ANOVA assumptions are reviewed during the BDRM and in case the assumptions are not fulfilled, data transformation and alternative methods are discussed (see sections 12.5.1.3 and 12.5.1.4).

In addition, the following analyses will be presented:

- Sensitivity analysis of the same analysis repeated for the FAS and mFAS
- Sensitivity analysis of spinal surgery subjects with no tumors.

